### 6.4. Blinding, Masking

This is an open-label study; potential bias will be reduced by central randomization.

# **6.5.** Study Intervention Compliance

Participants self-administer study intervention(s) at home, and compliance with study intervention will be assessed at each visit. Compliance will be assessed by direct questioning, during the site visits and documented in the source documents and relevant form. Deviation(s) from the prescribed dosage regimen should be recorded.

A record of the quantity of Cortison or Plenadren dispensed by the pharmacy to the participants and administered by each participant is available in the core record (kjernejournal),

### 6.6. Dose Modification

Participants will start on either 20 mg Plenadren once daily or 25 mg Cortisone divided in three daily doses. The Cortisone tablet can be divided into halves or quarters so that one half is given in the morning, a quarter at midday and a quarter in the afternoon (12.5 + 6.25 + 6.25 mg daily). Any dose modification can be made at the discretion of the study investigators. The study protocol includes measurement and cortisol in saliva and serum to aid clinicians in dose modification. Likewise we have developed ten clinical questions for the patients to clarify symptoms that may indicate a need for dose adjustment.

After one week serum cortisol will be sampled one and four hours after ingesting the morning dose to assess drug uptake. If a dose change is deemed necessary based on these results and clinical evaluation of the patient, the doses will be altered if necessary, and documented in the study files. If the patient develops symptoms and/or signs of overtreatment with glucocorticoid (unexpected weight gain, Cushingoid clinical signs), a dose reduction will be instituted at the investigators discretion, normally a 25% reduction in daily dose. Accordingly, if the patient has symptoms of undertreatment (i.e. debilitating fatigue, increased pigmentation) and post dose serum cortisol levels are low, a dose increase will be instituted at the investigators discretion, normally a 25% increase in daily dose.

© 2015-2021 TransCelerate BioPharma

Doc. No. CT 2.01.01. Valid from 31 Jan 2022. Only

Only the electronic version is valid.

Page 26 of 65

# 6.7. Continued Access to Study Intervention after the End of the Study

The patient will continue on Cortisone treatment after the study with the option to start or continue with Plenadren at the investigators discretion.

# 6.8. Prior and Concomitant Therapy

Any medication or vaccine (including over-the-counter or prescription medicines, recreational drugs, vitamins, and/or herbal supplements) that the participant is receiving at the time of enrollment or receives during the study, must be recorded along with:

- Reason for use
- Dates of administration including start and end dates
- Dosage information including dose and frequency

### 6.8.1. Rescue Medicine

The study site will not supply any form of study specific rescue medication. However, participants will be prescribed hydrocortisone for intramuscular use as per standard care, for use in case of an adrenal crisis. Occurrence of adrenal crisis will be documented at each study visit in the study-specific form. An adrenal crisis leading to admission will be registered as a SAE.

© 2015-2021 TransCelerate BioPharma

Doc. No. CT 2.01.01. Valid from 31 Jan 2022. Only the electronic version is valid.

Page 27 of 65

# 7. Discontinuation of Study Intervention and Participant Discontinuation/Withdrawal

# 7.1. Discontinuation of Study Intervention

Replacement therapy with either Plenadren or Cortisone is needed at all times. If a participant experience side-effects that might be related to ingredients in the tablet or do not obtain sufficient effect, other means of glucocorticoid replacement must be considered at the discretion of the investigator.

# 7.2. Participant Discontinuation/Withdrawal from the Study

- A participant may withdraw from the study at any time at the participant's own request for any reason (or without providing any reason).
- A participant may be withdrawn at any time at the discretion of the investigator for safety reasons.
- At the time of discontinuing from the study, if possible, an early discontinuation visit should be conducted, as shown in the SoA. See SoA for data to be collected at the time of study discontinuation and follow-up and for any further evaluations that need to be completed.
- The participant will be permanently discontinued from the study intervention and the study at that time.
- If the participant withdraws consent for disclosure of future information, the sponsor may retain and continue to use any data collected before such a withdrawal of consent.
- If a participant withdraws from the study, the participant may request destruction of any samples taken and not tested, and the investigator must document this in the site study records.

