### Objectives, Endpoints, and Estimands:

© 2015-2021 TransCelerate BioPharma

Doc. No. CT 2.01.01. Valid from 31 Jan 2022. Only the electronic version is valid.

Page 8 of 65

**Overall design:** Registry-based, open-label, single center, randomized, controlled academic investigational medicine study.

**Brief Summary:** The purpose of this study is to compare quality of life, metabolic parameter, bone health and sleep quality with Plenadren or Cortisone in patients with primary adrenal insufficiency.

**Treatment duration**: 12 months

Visit number and frequency: 6 visits

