# CONFIDENTIAL The CORTAD study Clinical Trial Protocol version6.2, 15thNovember 2023

Procedure	ng ation			Intervention Period				
	Screening	Randomization	Baseline	Phone visit	Lab visit			
Visit number	1		2	3	4	5	6	7
Diagnostic laboratory tests adrenal insufficiency 	X							
Laboratory tests (hematology, electrolytes, creatine, liver enzymes, cholesterols and triglycerides, HbA1c, cobalamine, , ferritin, renin, aldosterone, 25OH vitamin D, TSH, FT4)			X			X	X	
HOMA index (insulin and glucose)			X			X	X	
Serum and EDTA samples for Biobanking forc- peptide, bone markers, BDNF, metylmalomic acid and autoantibody screening (etiology and autoimmune comorbidity)			X			X	X	
Urine sample (steroid metabolome)							X	
Hair sample (cortisol)			X				X	
HRQoL questionnaires (RAND-36, AddiQoL-30)			X		X	X	X	
Cognitive tests	X					X	X	
Bone mineral density and body composition					X		X	
Blood sampling 1 and 4 h after morning dose (S-cortisol)					X			
Dose adjustment according to S-cortisol (if applicable) 					X			
Saliva cortisol (before, +1h and +4 h after morning dose						X	X	

© 2015-2021 TransCelerate BioPharma

Doc. No. CT 2.01.01. Valid from 31 Jan 2022.

Only the electronic version is valid.

Page 12 of 65

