# CONFIDENTIAL The CORTAD study Clinical Trial Protocol version6.2, 15thNovember 2023

Procedure	gu	ation			Inter	rvention Period		End of study 
	Screening	Randomization	Baseline	Phone visit	Lab visit			
Visit number	1		2	3	4	5	6	7
Review dosing and compliance				X		X	X	
Register the use of extra doses (oral or i.m./i.v.; for 4 weeks)						X	X	
Evaluation of sleep (Sleep diary, Actigraphy)						_======	=====	
Working ability (sick leave, sick pension)			X				X	
Sleep radar (Somnofy)							X	
AE review			X		_=====================================			X
SAE review			X					X
Register any adrenal crisis symptoms or treatment (separate form)			X					
Concomitant medication review			X				=====	
Noklus study form completion	X		X	X	X	X	X	X

<sup>1 Register reason for screening failure, if applicable

© 2015-2021 TransCelerate BioPharma

Doc. No. CT 2.01.01. Valid from 31 Jan 2022.

Only the electronic version is valid.

Page 13 of 65

<sup>2 Diagnostic laboratory tests (21-OH-autoantibody, cortisol, ACTH, aldosterone, renin, cosyntropin stimulated cortisol if available)

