# 8. Study Assessments and Procedures

- Study procedures and their timing are summarized in the SoA (for time line se figure on page 22). eCRF forms are generated using the Fasttrack infrastructure and is available in Endojournal and Noklus Diabetes at every hospital, one form per visit (visits 1-6). Protocol waivers or exemptions are not allowed.
- Adherence to the study design requirements, including those specified in the SoA, is essential and required for study conduct.
- All screening evaluations must be completed and reviewed to confirm that potential
  participants meet all eligibility criteria. The investigator will maintain a screening log to
  record details of all participants screened and to confirm eligibility or record reasons for
  screening failure, as applicable.
- Procedures conducted as part of the participant's routine clinical management (ie, hormone levels at diagnosis, 21-OH autoantibodies, blood count, renal function, glucose, electrolytes, lipids) obtained before signing of the ICF may be utilized for screening or baseline purposes provided the procedures met the protocol-specified criteria and were performed within the timeframe defined in the SoA.
- In the event of a significant study-continuity issue (e.g., caused by a pandemic), alternate strategies for participant visits, assessments, medication distribution and monitoring may be implemented by the sponsor or the investigator, as per local health authority/ethics requirements.

The maximum amount of blood collected from each participant over the duration of the study, including any extra assessments that may be required, will not exceed 500 mL.

Repeat or unscheduled samples may be taken for safety reasons or for technical issues with the samples.

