## 8.4.1. Time Period and Frequency for Collecting AE and SAE Information

All SAEs and AEs will be collected from the start of study intervention until visit 6 at the time points specified in the SoA (Section 1.3).

All SAEs will be recorded and reported to the sponsor or designee immediately and under no circumstance should this exceed 24 hours, as indicated in Appendix [3/7]. The investigator will submit any **updated SAE data to the sponsor within 24 hours** of it being available.

Investigators are not obligated to actively seek information on AEs or SAEs after conclusion of the study participation. However, if the investigator learns of any SAE, including a death, at any time after a participant has been discharged from the study, and the investigator considers the

© 2015-2021 TransCelerate BioPharma

Doc. No. CT 2.01.01. Valid from 31 Jan 2022.

Only the electronic version is valid.

Page 39 of 65

event to be reasonably related to the study intervention or study participation, the investigator must promptly notify the sponsor.

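### Section 7.2 relies on the Schedule of Activities for the early discontinuation visit, but the schedule has no such visit and asks for no HRQoL at exit, so a participant leaving between visits gives no exit score on the primary endpoint

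*Protocol*

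**What the plan says.** Section 7.2 of the protocol states that, where possible, "an early discontinuation visit should be conducted, as shown in the SoA". It specifies no content of its own and passes that to the same table: "See SoA for data to be collected at the time of study discontinuation and follow-up and for any further evaluations that need to be completed". It then ends both study treatment and study participation at that point, so no later scheduled assessment follows.

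The SoA in section 1.3 has columns for screening, randomization, baseline (visit 2) and visits 3 to 7. None is labelled early discontinuation. Visit 7 is headed as the end of study and has no day or week. The marks legible in that column are AE review, SAE review and "Noklus study form completion". The HRQoL row, which covers RAND-36 and AddiQoL-30, is marked at visits 2, 4, 5 and 6 and is blank at visit 7.

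Three other places do not recognise a visit 7:
- Synopsis: "Visit number and frequency: 6 visits".
- Section 8, on the electronic forms: "one form per visit (visits 1-6".
- Section 8.4.1: "All SAEs and AEs will be collected from the start of study intervention until visit 6".

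**The concern.** The two questionnaires are the primary endpoint instruments (section 3). A site that follows section 7.2 looks in the SoA for what to collect and finds either nothing or an end-of-study column without them. The participant attends, safety data are taken, and the primary outcome is not measured although the opportunity was there.

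This matters because exit can be related to outcome. Appendix 1 (section 10.1) withdraws participants who have serious adverse events, and section 6.8.1 classes an adrenal crisis leading to admission as an SAE. The trial is open-label (section 6.4) with a self-reported primary endpoint, so reasons for leaving could differ between arms. A score taken at exit is the most recent evidence on how such a participant was doing. A statistical analysis plan can decide how to use that score but cannot recover one that was never collected.

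**Working it through.** **Step 1: follow the cross-reference.** The table reads the SoA column by column.

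| Item | V2 | V3 | V4 | V5 | V6 | V7 |
|---|---|---|---|---|---|---|
| Day | 0 | 7 | 28 | 182 | 365 | none |
| AddiQoL-30 and RAND-36 | X | – | X | X | X | – |

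The text was extracted from PDF and some rows that span several visits are damaged (AE, adrenal crisis and concomitant medication). The HRQoL row is intact. Section 8.2.1 confirms it independently by placing both questionnaires at baseline and 1, 6 and 12 months only. Sections 8.1.1 to 8.1.3 describe visits 1 to 6 and no discontinuation visit.

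**Step 2: set visit 7 against the rest of the protocol.**
- SoA: visit 7 exists, with a form and AE/SAE review.
- Synopsis: six visits.
- Section 8: forms for visits 1 to 6, so none for visit 7.
- Section 8.4.1: AE and SAE collection ends at visit 6, so the review at visit 7 falls outside the stated period.

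These statements cannot all hold as written.

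**Step 3: how old the last score can be.**
- Leaving just before visit 5: 182 − 28 = 154 days, about 5 months.
- Leaving just before visit 6: 365 − 182 = 183 days, about 6 months.

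Both are maxima. Someone who leaves at or near visit 4, 5 or 6 has a current score.

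**Step 4: how many participants.** Section 9.3 takes 21 per group and 10% dropout. From 42 participants, 42 × 1.1 = 46.2 (or 42 / 0.9 = 46.7), which agrees with the stated minimum of 46 to within one participant. At 10%, leavers number 0.10 × 46 = 4.6 or 0.10 × 50 = 5. This is a ceiling for the gap, because some leavers exit at a scheduled visit and some never attend an exit visit.

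**Step 5: effect on the primary analysis.** Objective 1.1 in section 9.1 uses a linear mixed model for repeated measures. It keeps every score a leaver gave before exit. What is lost is the score at exit. The protocol gives neither dropout by arm nor the change in score before exit, so no bias can be computed from it.

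**The case against.** The strongest reply is that little is lost. Leavers keep their earlier scores and the mixed model uses them. Section 7.2 makes the exit visit conditional on feasibility, and people lost to follow-up (section 7.3) attend none, so an extra SoA column would not reach them. An exit score is also off schedule and is not a 6- or 12-month value. All of this stands, and it limits the point to a few participants.

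A reader might infer three stronger things that the protocol does not support.

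- **That everyone who drops out lacks primary-endpoint data.** They do not: earlier scores remain, and some exits fall at a scheduled visit.
- **That insufficient effect under section 7.1 removes participants from the study.** That section concerns changing the replacement drug and does not say that the participant leaves. The route the text does give is the SAE rule in Appendix 1, besides the participant's own request and the investigator's safety decision in section 7.2.
- **That a numerical bias follows.** Suppose five leavers had true scores 4 to 8 points below their last record. With 25 per arm and a 4:1 split, the treatment difference shifts by (4 − 1)/25 × 4 to 8 = 0.48 to 0.96 points. A 3:2 split gives 1/25 × 4 to 8 = 0.16 to 0.32, and equal losses give none. Both the split and the decline are invented, and the sum carries the last score forward, which the protocol does not plan. Its listed missing-data methods are complete case, worst/best case and multiple imputation (section 9.2.1).

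It can also be said that the visit 7 mismatch is only administrative. On its own it is. It matters here because visit 7 is the only column that section 7.2 could be pointing to.

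**Conclusion.** The point holds as a gap in data collection that is cheap to close. Section 7.2 refers to a visit that the SoA does not contain, and the only candidate column omits both primary-endpoint instruments and conflicts with three other statements in the protocol. A participant who leaves between visits and attends the exit visit gives no AddiQoL-30 or RAND-36 score there.

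Its reach is at most about 5 of 50 participants at the protocol's own 10% dropout, with a last score at most 154 or 183 days old. The conclusion rests on the intact HRQoL row and on section 8.2.1, not on the damaged rows of the SoA. That exit is related to outcome or differs by arm is plausible from Appendix 1 and the open-label design, but it is not shown. The protocol does not support a bias figure, and none is claimed.

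**What to change.** - Define visit 7 as the early discontinuation visit, or add a column with that label. Mark it for AddiQoL-30, RAND-36, AE/SAE review, adrenal crisis review and form completion, and provide the form.
- Reconcile the synopsis visit count, the range of forms in section 8, the visit descriptions in section 8.1.3 and the AE collection period in section 8.4.1 with that decision.
- State that an exit score enters the mixed model or the multiple imputation at its actual time and is not treated as a 6- or 12-month value. If the model treats visits as categories, the score can serve as an auxiliary variable in the imputation.

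The cost is one extra form, two questionnaires for a few participants at a visit that section 7.2 already requests, and an off-schedule time point to handle in the analysis. The change does not help with participants who cannot be reached.

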## 8.3.4. Pregnancy Testing

Pregnancy testing should be done if menstruation stops or becomes irregular. If pregnancy is confirmed, the participant should be withdrawn from the study.

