### 8.4.5. Pregnancy

Pregnancy at screening and planned pregnancy during the duration of study
participation is an exclusion criteria. However, all AD patients (including all study
participants) need to continue using one of the study drugs throughout the pregnancy
as cortisol is a hormone necessary for survival in this patient group. The two study
drugs in this study are the only approved treatment options in Norway. Therefore,

© 2015-2021 TransCelerate BioPharma

Doc. No. CT 2.01.01. Valid from 31 Jan 2022. Only the electronic version is valid.

Page 40 of 65

study participants who become pregnant during this trial will not be discontinued from study treatment.

- Pregnant AD patients may need alterations of doses which will be performed by local study investigators independently of study participation.
- If a pregnancy is reported during the study, the investigator will record pregnancy information in the appropriate form and submit it to the sponsor.
- While pregnancy itself is not considered to be an AE or SAE, any pregnancy complication or elective termination of a pregnancy for medical reasons will be reported as an AE or SAE.
- Abnormal pregnancy outcomes (e.g. spontaneous abortion, fetal death, stillbirth, congenital anomalies, ectopic pregnancy) are considered SAEs and will be reported as such.

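### Read literally, 7.2 ends the study drug for anyone who leaves the study, which conflicts with 7.1 and with the pregnancy rules in 8.3.4 and 8.4.5

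*Protocol*

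**What the plan says.** Section 7.2 lists how a participant may leave the study (own request, or the investigator's decision on safety grounds), asks for an early discontinuation visit where possible, and then states: "The participant will be permanently discontinued from the study intervention and the study at that time". It gives no exception.

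Section 7.1, which deals with the drug rather than the study, opens with "Replacement therapy with either Plenadren or Cortisone is needed at all times". For side-effects possibly due to tablet ingredients, or for insufficient effect, it says "other means of glucocorticoid replacement must be considered at the discretion of the investigator". It does not say whether such a participant stays in follow-up.

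Three other sections bear on the same question:

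- Section 8.3.4: "If pregnancy is confirmed, the participant should be withdrawn from the study".
- Section 8.4.5 says that the two "drugs in this study are the only approved treatment options in Norway", and that "study participants who become pregnant during this trial will not be discontinued from study treatment".
- Section 6.7: "The patient will continue on Cortisone treatment after the study with the option to start or continue with Plenadren at the investigators discretion".

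Table 6.1 labels both Cortison and Plenadren as investigational products. Section 6.1 describes both as marketed drugs prescribed in the ordinary way by the treating endocrinologist.

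**The concern.** The 7.2 sentence suits a trial in which the study drug is an added, experimental treatment. Here the study intervention is the patient's replacement hormone. A rule that couples leaving the study with ending the drug therefore meets other sections that require replacement to go on.

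Two things are at stake. The first is that sites have instructions they cannot all follow, on a matter of clinical management. The second concerns the data. Section 7.2 does not distinguish stopping the assigned drug from ceasing to be followed, and 7.1 leaves follow-up after a change of drug open. If some sites treat a change of drug as leaving the study, patients who change because the drug did not work well enough stop contributing quality-of-life scores. In an open-label trial with a patient-reported primary endpoint, that loss could relate to the outcome and could differ between arms.

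**Working it through.** No formula applies to the contradiction itself, so the check sets the sections side by side.

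**Step 1: what 7.2 covers.** Table 6.1 makes both products investigational, so the study intervention is Cortisone for one arm and Plenadren for the other. The 7.2 rule covers either arm and any reason for leaving.

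**Step 2: 7.2 against 7.1.** If study intervention means both products, 7.2 ends what 7.1 says is always needed. If it means only the assigned product, both rules can be met literally only by moving each leaver to the other arm's drug, which no section states. The other means of replacement in 7.1 are tied to side-effects or insufficient effect. They do not cover a participant who simply wants to stop taking part.

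**Step 3: the pregnancy chain.**

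1. Section 8.3.4: confirmed pregnancy leads to withdrawal from the study.
2. Section 7.2: withdrawal from the study permanently ends the study intervention.
3. Section 8.4.5: study treatment is not ended in pregnancy.

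As written, the first two steps contradict the third. This is the clearest case, because each section is explicit.

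**Step 4: 7.2 against 6.7.** Section 6.7 provides for treatment after the study with Cortisone, or with Plenadren at the investigator's discretion. It does not mention early leavers. A Cortisone participant who leaves early is taken off the drug by 7.2, while 6.7 would have the same patient stay on it once the study is over.

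**Step 5: how many participants the rule reaches.** Inputs: 50 participants (1.1) and a 10% drop-out rate (9.3). 50 × 0.10 = 5 leavers. Other sections also lead into 7.2: 10.1 withdraws participants who have a serious adverse event or come to meet an exclusion criterion, and 7.3 treats unreachable participants as withdrawn. The plan does not say whether its 10% includes these.

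**Step 6: what follows for the primary comparison.** The 7.2 rule runs in one direction: leaving the study ends the drug. It does not say that changing the drug ends study participation. That case falls under 7.1, which is silent on follow-up. So the protocol does not order the loss of patients who change drug, but neither does it tell sites to keep assessing them.

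**Step 7: can a bias be computed?** It would need the proportion in each arm who change drug and then leave follow-up, and how far their scores differ from the rest. The protocol gives neither. The 10% in 9.3 is overall drop-out, not change of drug in one arm. Table 4 in 9.1 plans a linear mixed model, which uses scores collected before a patient leaves, so a shift in a simple observed mean would not describe the planned analysis. No figure is given here.

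**The case against.** The strongest reply is that nobody would be taken off replacement. Section 2.3.1 says participants would be offered one of the two therapies whether or not they take part. Sections 6.1 and 6.2 describe ordinary prescription and pharmacy supply, so leaving the study cuts off no study-supplied drug. Section 6.7 provides for either drug afterwards, and 10.1.9 asks the investigator to assure suitable therapy if the study stops early. On this view 7.2 ends only the protocol assignment. That is very likely the intent, and it answers the stronger reading a reader might infer, that the protocol puts uninterrupted replacement in real danger. The documents do not support that reading.

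The wording still fails. Section 7.2 contains no such limit, and the milder reading has to give study intervention in 7.2 a different sense from study treatment in 8.4.5. Section 8 requires adherence and allows no waivers, so sites should not have to supply the exception themselves.

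A second reply is that the protocol already keeps stopping the drug (7.1) apart from leaving the study (7.2), and that the handling of drug changes in the analysis belongs in the statistical analysis plan. The first half stands: a reader might infer that 7.2 drops patients who change drug from the quality-of-life comparison, and it does not say that. The second half stands for the analysis but not for data collection, since an analysis plan cannot recover questionnaires that were never collected.

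**Conclusion.** The contradiction stands. The 7.2 sentence, read literally, conflicts with 7.1 and, through 8.3.4, with 8.4.5; it also sits badly with 6.7. It is a stated rule that clashes with other stated rules, not a missing detail. It reaches about 5 of 50 participants at the plan's own drop-out rate, assuming that rate describes all leavers.

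The safety consequence is limited, because both drugs are ordinary prescriptions that continue outside the study. The consequence for bias is conditional: it arises only if sites handle a change of drug as withdrawal, which the protocol neither orders nor rules out. Its size cannot be derived from the documents. The point merits correction because the remedy is small and protects the primary endpoint. It does not show that the trial's result would be wrong. No view is taken here on which treatment rule is right.

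**What to change.** 1. The sponsor should reconcile 7.2 with 7.1, 6.7, 8.3.4 and 8.4.5 so that all five can be followed together. What happens to treatment on leaving the study, and in pregnancy, is for the clinical authors to word.
2. Record two events separately, each with its date and reason: change or stop of the assigned drug, and withdrawal from study follow-up.
3. State in 7.1 that after a change of drug the scheduled quality-of-life and safety assessments continue to month 12, unless the participant withdraws from follow-up.

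The cost is a short amendment and one added field on the study form. No visits are added to the schedule, and the sample size does not change.
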